### 3.2.6 Prior Therapy

Patients must have fully recovered from the acute toxic effects of all prior chemotherapy, immunotherapy, or radiotherapy prior to entering this study.

- 3.2.6.1 Myelosuppressive chemotherapy:
- 3.2.6.1.1 Solid Tumors:  
Patients with solid tumors must not have received myelosuppressive chemotherapy within 3 weeks of enrollment onto this study (6 weeks if prior nitrosourea).
- 3.2.6.2 Hematopoietic growth factors: At least 7 days must have elapsed since the completion of therapy with a growth factor. At least 14 days must have elapsed after receiving pegfilgrastim.
- 3.2.6.3 Anti-cancer agents not known to be myelosuppressive (e.g. not associated with reduced platelet or ANC counts):  $\geq 7$  days after the last dose of agent. See DVL homepage for commercial and investigational agent classifications. For agents not listed, the duration of this interval must be discussed with the study chair and the study-assigned Research Coordinator prior to enrollment.
- 3.2.6.4 Antibodies:  $\geq 21$  days must have elapsed from infusion of last dose of antibody, and toxicity related to prior antibody therapy must be recovered to Grade  $\leq 1$ .
- 3.2.6.5 Radiotherapy:  $\geq 2$  weeks must have elapsed since local palliative XRT (small port);  $\geq 6$  weeks must have elapsed since treatment with therapeutic doses of MIBG;  $\geq 3$  months must have elapsed if prior craniospinal XRT was received, if  $\geq 50\%$  of the pelvis was irradiated, or if TBI was received;  $\geq 6$  weeks must have elapsed if other substantial bone marrow irradiation was given.
- Subjects should not have any clinically relevant ongoing complications from prior radiation therapy (i.e., radiation esophagitis or other inflammation of the viscera).
- 3.2.6.6 Stem Cell Transplant or Rescue without TBI: No evidence of active graft vs. host disease and  $\geq 2$  months must have elapsed since transplant.
- 3.2.6.7 Study specific limitations on prior therapy: Not previously received XL184 or another MET/HGF inhibitor (tivantinib or crizotinib). There are no limits on number of prior therapeutic regimens. Patients who have been treated with prior VEGF pathway, or RET inhibitors (except XL184) may be eligible.

### 3.2.7 Organ Function Requirements

- 3.2.7.1 Adequate Bone Marrow Function Defined As:
- 3.2.7.1.1 For patients with solid tumors without bone marrow involvement:
- Peripheral absolute neutrophil count (ANC)  $\geq 1000/\mu\text{L}$
  - Platelet count  $\geq 100,000/\mu\text{L}$  (transfusion independent, defined as not receiving platelet transfusions within a

7 day period prior to enrollment)

- Hemoglobin  $\geq$  8.0 g/dL (may receive RBC transfusions).

3.2.7.1.2 For patients with solid tumors and known bone marrow metastatic disease:

- Peripheral absolute neutrophil count (ANC)  $\geq$  750/ $\mu$ L
- Platelet count  $\geq$  50,000/ $\mu$ L
- Hemoglobin  $\geq$  8.0 g/dL

Transfusions are permitted to meet both the platelet and hemoglobin criteria. Patients must not be known to be refractory to red blood cell or platelet transfusions.

3.2.7.2 Adequate Renal Function Defined As:

- Creatinine clearance or radioisotope GFR  $\geq$  70 mL/min/1.73 m^2 **or** a serum creatinine based on age/gender as follows:

Age	Maximum Serum Creatinine (mg/dL)	
	Male	Female
2 to < 6 years	0.8	0.8
6 to < 10 years	1	1
10 to < 13 years	1.2	1.2
13 to < 16 years	1.5	1.4
$\geq$ 16 years	1.7	1.4

The threshold creatinine values in this Table were derived from the Schwartz formula for estimating GFR (Schwartz et al. J. Peds, 106:522, 1985) utilizing child length and stature data published by the CDC.

- Urine protein:  $\leq$  30 mg/dl in urinalysis or  $\leq$  1+ on dipstick, unless quantitative protein is < 1000 mg in a 24 h urine sample

3.2.7.3 Adequate Liver Function Defined As:

- Total bilirubin  $\leq$  1.5 x upper limit of normal (ULN) for age
- SGPT (ALT)  $\leq$  135 U/L (3x ULN) (for the purpose of this study, the ULN for SGPT is 45 U/L)
- Serum albumin  $\geq$  2.8 g/dL.

3.2.7.4 Adequate Cardiac Function Defined As:

- No history of congenital prolonged QTc syndrome, NYHA Class III or IV congestive heart failure (CHF).
- No clinically significant cardiac arrhythmias, stroke or myocardial infarction within 6 months prior to enrollment.
- QTc  $\leq$  480 msec. Note: Patients with Grade 1 prolonged QTc (450- 480 msec) at the time of study enrollment should have correctable causes of prolonged QTc addressed if possible (i.e., electrolytes, medications).

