## 3.2 Eligibility: Inclusion Criteria

**Important note: The inclusion criteria listed below are interpreted literally and cannot be waived. All clinical and laboratory data required for determining eligibility of a patient enrolled on this trial must be available in the patient's medical/research record. These source documents must be available for verification at the time of audit.**

**All clinical and laboratory studies to determine eligibility must be performed within 7 days prior to enrollment unless otherwise indicated. Laboratory values used to assess eligibility must be no older than seven (7) days at the start of therapy. Laboratory tests need not be repeated if therapy starts within seven (7) days of obtaining labs to assess eligibility. If a post-enrollment lab value is outside the limits of eligibility, or laboratory values are > 7 days old, then the following laboratory evaluations must be re-checked within 48 hours prior to initiating therapy: CBC with differential, bilirubin, ALT (SGPT) and serum creatinine. If the recheck is outside the limits of eligibility, the patient may not receive protocol therapy and will be considered off protocol therapy. Imaging studies, bone marrow biopsy and/or aspirate, if applicable, must be obtained within 2 weeks prior to start of protocol therapy (repeat the tumor imaging if necessary).**

3.2.1 Age: Patients must be  $\geq 2$  and  $\leq 30$  years of age at the time of study entry for all strata except upper age limit of  $\leq 18$  years of age for MTC, RCC and HCC.

3.2.2 Body Surface Area (BSA): Patients must have a body surface area  $\geq 0.35$  m^2.

3.2.3 Diagnosis: Patients must have recurrent or refractory disease, or newly diagnosed disease with no known curative therapy or therapy proven to prolong survival with an acceptable quality of life. Patients must have had histologic verification of one of the malignancies listed below at original diagnosis or at relapse.

- Ewing sarcoma
- Rhabdomyosarcoma (RMS)
- Non-rhabdomyosarcoma soft tissue sarcomas (STS) including microphthalmia transcription factor associated STS (alveolar soft part sarcoma (ASPS) and clear cell sarcoma (CCS))
- Osteosarcoma
- Wilms tumor
- Rare tumors
  - Medullary thyroid carcinoma (MTC)

- Renal cell carcinoma (RCC)
- Hepatocellular carcinoma (HCC)
- Hepatoblastoma
- Adrenocortical carcinoma

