#### 5.1.1 Non-Hematological Dose-Limiting Toxicity

- Any Grade 4 non-hematological toxicity
- Any Grade 3 non-hematological toxicity with the specific exception of:
  - Grade 3 nausea and vomiting of less < 3 days duration
  - Grade 3 diarrhea  $\leq$  3 days duration
  - Grade 3 liver enzyme elevation including ALT/AST/GGT/bilirubin that return to levels that meet initial eligibility criteria within 7 days of study drug interruption and that do not recur upon re-challenge with study drug. Note: For the purposes of this trial the ULN for ALT is defined as 45 U/L and the ULN for AST is defined as 50 U/L. See [Section 5.7](#) for dose modifications for liver toxicity. Adverse event grades will be based on increases above the upper limit of normal, regardless of the subject's baseline. See appendix XI for toxicity-specific grading table.
  - Grade 3 fever or infection < 5 days duration.
  - Grade 3 hypophosphatemia, hypokalemia, hypocalcemia and/or hypomagnesemia responsive to supplementation
  - Grade 3 asymptomatic amylase or lipase elevation that resolves to Grade 1 within 7 days of study drug interruption and that does not recur upon re-challenge with XL184. See [Section 5.8](#) for dose modifications for pancreatic toxicity.
  - Grade 3 proteinuria (urine protein/creatinine (P/C) ratio > 1.9) unless it is confirmed with a second measurement within 72 hours
- Any Grade 2 non-hematological toxicity that persists for  $\geq$  7 days and is considered sufficiently medically significant or sufficiently intolerable by patients that it requires treatment interruption
- Dose-limiting hypertension
  - Any Grade 4 hypertension
  - A blood pressure > 25 mmHg above the ULN confirmed by repeated measurement on the same day is dose limiting. For pediatric patients ULN is the 95th percentile for age, height, and gender ([Appendix V](#)) and for patients  $\geq$  18 years of age ULN is 140/90 mmHg.
  - In patients who begin antihypertensive therapy a blood pressure > 10 mmHg but  $\leq$  25 mmHg above the ULN ([Appendix V](#)) for > 14 days is dose limiting.
- QTc prolongation > 500 ms that persists despite correction of serum electrolyte abnormalities will be considered dose limiting

- Grade 2 or higher allergic reactions that necessitate discontinuation of study drug will not be considered a dose-limiting toxicity.

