### 5.2 **Dose Modifications for Hematological Toxicity**

The Study Chair must be notified of any dosage modification or use of myeloid growth factor. If a patient's dose is reduced due to toxicity, any future XL184 total weekly dose should not exceed a dose that was previously not tolerated.

- 5.2.1 If a patient experiences Grade 4 neutropenia or Grade 4 thrombocytopenia, the treatment will be held. Counts should be checked twice weekly during this time. If the toxicity resolves to meet eligibility parameters within 21 days of drug discontinuation, the patient may resume treatment at the next lower dose level (see [Section 5.11](#)). Doses reduced for toxicity will not be re-escalated, even if there is minimal or no toxicity with the reduced dose.
- 5.2.2 If toxicity does not resolve to meet eligibility parameters within 21 days of drug discontinuation, the patient must be removed from protocol therapy.
- 5.2.3 Two dose reductions will be allowed for toxicity. If a patient experiences a dose limiting toxicity after two dose reductions, they must be removed from protocol therapy. For patients with BSA 0.35-0.39, only 1 dose reduction will be allowed as the lowest weekly administered dose is 60 mg/week.

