#### 5.4 Dose Modifications for Proteinuria

Proteinuria has been reported with XL184 in adult studies and pediatric trial ADVL1211.

[figure not shown]
- If urinalysis shows  $\geq$  trace protein then obtain UPC.
- If the urine protein/creatinine (P/C) ratio  $\leq 1.9$  continue XL184. If patient has Grade 3 proteinuria (urine protein/creatinine (P/C) ratio  $> 1.9$ ), a second measurement should be obtained within 72 hours. A second confirmation of Grade 3 proteinuria will be considered a DLT.
- If the second measurement confirms Grade 3 proteinuria (urine protein/creatinine (P/C) ratio  $> 1.9$ ), then interrupt XL184 treatment and re-assess weekly.
- If XL184 is held for  $\geq 21$  days then remove from protocol therapy. If the urine protein/creatinine (P/C) ratio decreases to  $\leq 1.9$  in  $< 21$  days then resume XL184 at a lower dose as outlined in [Section 5.11](#).
- Monitor the UPC weekly for 2 consecutive weeks once protocol therapy resumes.

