### 11.4 **Reporting Requirements for Specialized AEs**

#### 11.4.1 Baseline AEs

Although a pertinent positive finding identified on baseline assessment is not an AE, when possible it is to be documented as “Course Zero” using CTCAE terminology and grade. An expedited AE report is not required if a patient is entered on a protocol with a pre-existing condition (e.g., elevated laboratory value, diarrhea). The baseline AE must be re-assessed throughout the study and reported if it fulfills expedited AE reporting guidelines.

- a. If the pre-existing condition worsens in severity, the investigator must reassess the event to determine if an expedited report is required.
- b. If the AE resolves and then recurs, the investigator must re-assess the event to determine if an expedited report is required.
- c. No modification in grading is to be made to account for abnormalities existing at baseline.

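### The fixed 24-hour urine protein override at entry is not scaled to body size, so a small child can be eligible while already above the protocol's own UPC threshold for holding XL184

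*Combined protocol and SAP*

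**What the plan says.** **Entry.** Section 3.2.7.2 limits urine protein to 30 mg/dL on urinalysis or 1+ on dipstick. A patient over that limit still qualifies through an override: "unless quantitative protein is < 1000 mg in a 24 h urine sample". The amount is not expressed per m², per kg or relative to creatinine. No UPC limit appears among the entry criteria, and Section 3.2 states that the criteria are applied literally and may not be waived.

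**Who it applies to.** Section 3.2.1 admits patients from 2 to 30 years of age (to 18 for three tumor types). Section 3.2.2 begins "Patients must have a body surface area" and sets the minimum at 0.35 m². The smallest band is planned for explicitly: "For patients with BSA 0.35-0.39, only 1 dose reduction will be allowed" (Section 5.2.3).

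**On treatment.** Section 5.4 tells sites that, at or above "trace protein then obtain UPC". A UPC of 1.9 or less allows treatment to continue. A higher value is Grade 3 and is repeated within 72 hours. Section 5.1.1 lists as an exception to the dose-limiting toxicity (DLT) definition "Grade 3 proteinuria (urine protein/creatinine (P/C) ratio > 1.9) unless it is confirmed with a second measurement within 72 hours". Section 5.4 adds: "A second confirmation of Grade 3 proteinuria will be considered a DLT". XL184 is then interrupted.

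**Baseline findings.** Section 11.4.1 says that a positive finding at baseline is not an adverse event and is documented as course zero where possible. Item c adds: "No modification in grading is to be made to account for abnormalities existing at baseline".

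**The concern.** The entry limit is a total daily amount and the on-treatment limit is a ratio to creatinine. How they relate depends on how much creatinine the patient excretes, and that falls with body size. In an adult-sized patient the 1000 mg limit is the stricter of the two. In a small child the order reverses, and the same urine can satisfy Section 3.2.7.2 and exceed the threshold in Sections 5.1.1 and 5.4.

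Other limits nearby are adjusted: GFR is per 1.73 m², serum creatinine is set by age and sex (both Section 3.2.7.2), and blood pressure is set by age, height and gender (Section 3.2.7.6). The urine protein override is not adjusted, and nothing in the protocol reconciles it with the UPC threshold.

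At stake is the consistency of the rules for the youngest patients. A child could be enrolled under one section and, at the first UPC and its repeat, meet the level at which another section requires interruption. The mismatch can also recur, because Section 4.1.3 reuses the Section 3.2.7 laboratory limits for starting each cycle.

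**Working it through.** The plan gives no derived figure on this point to reproduce. The check converts one limit into the units of the other.

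**Inputs from the protocol:** 24-hour protein below 1000 mg (Section 3.2.7.2); UPC above 1.9 (Sections 5.1.1 and 5.4); minimum body surface area (BSA) 0.35 m² (Section 3.2.2); GFR of at least 70 mL/min/1.73 m², and maximum serum creatinine 0.8 mg/dL at ages 2 to under 6 (Section 3.2.7.2).

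**Assumption:** the protocol gives no daily creatinine excretion. I take 10 to 25 mg/kg/day and show the whole range. The body weights are illustrations.

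**Step 1, where the limits coincide.** UPC = 24-hour protein / 24-hour creatinine. Setting protein to 1000 mg and UPC to 1.9 gives 1000 / 1.9 = 526 mg creatinine per day. Below that excretion, protein under 1000 mg can coexist with a UPC above 1.9.

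**Step 2, break-even weight** = 526 / excretion rate:

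| Assumed rate (mg/kg/day) | Break-even weight (kg) |
|---|---|
| 10 | 52.6 |
| 15 | 35.1 |
| 20 | 26.3 |
| 25 | 21.1 |

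**Step 3, UPC at 999 mg protein** = 999 / (weight × rate):

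| Weight | At 10 mg/kg/day | At 25 mg/kg/day |
|---|---|---|
| 11 kg | 999/110 = 9.1 | 999/275 = 3.6 |
| 20 kg | 999/200 = 5.0 | 999/500 = 2.0 |
| 60 kg | 999/600 = 1.7 | 999/1500 = 0.7 |

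Up to about 20 kg the UPC exceeds 1.9 over the whole assumed range. At 60 kg it does not exceed 1.9 anywhere in it.

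**Step 4, width of the overlap.** The protein that corresponds to UPC 1.9 is 1.9 × weight × rate. At 11 kg this is 209 mg (10 mg/kg/day) to 523 mg (25 mg/kg/day), so the overlap runs from there up to 1000 mg. At 20 kg it is 380 to 950 mg, so at the high rate only a narrow band remains.

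**Step 5, a cross-check without the per-kg assumption.** Excretion (mg/day) = clearance × BSA/1.73 × 14.4 × serum creatinine, where 14.4 converts mL/min to dL/day.

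- Protocol figures, 70 mL/min/1.73 m² and 0.8 mg/dL: at 0.35 m², 70 × 0.35/1.73 × 14.4 × 0.8 = 163 mg/day, UPC 999/163 = 6.1. At 0.50 m², 233 mg/day, UPC 4.3. Break-even BSA is 1.13 m².
- Assumed high clearance of 150 mL/min/1.73 m² with 0.8 mg/dL: UPC 2.9 at 0.35 m² and 2.0 at 0.50 m². Break-even BSA is 0.53 m².

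These pairings are illustrations, not bounds: the GFR figure is a minimum, the creatinine figure a maximum, and the criteria are alternatives. Both still put the smallest eligible children above 1.9.

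**The case against.** The arithmetic is hard to dispute. The strongest reply concerns its consequences, and much of it stands.

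- **A reader might infer that such a child enters with a DLT.** The protocol does not say so. Section 5.1 requires at least possible attribution to XL184, and Section 5.1.1 requires confirmation within 72 hours. Proteinuria documented before the first dose does not meet the attribution requirement by itself.
- **A reader might infer from Section 11.4.1c that baseline proteinuria will be counted in the toxicity tables and the Section 9.3.4 monitoring rule.** Item c governs grading. The same section says that a baseline finding is not an adverse event and is reassessed during the study. Section 9.3.4 names proteinuria without a grade, baseline or attribution rule, so counting is possible but not established.
- **A reader might infer that the case would go unnoticed.** Section 4.2.2 item d requires urinalysis before Cycle 1 and points to Section 5.4, whose UPC trigger is trace protein. Anyone using the override is over the urinalysis or dipstick limit, so detection is probable. It would come through a dose-modification rule, though, and the child would remain eligible.
- **A reader might take the break-even weights to mean that every child below them is affected.** They show only where coexistence is possible. The patient must also fail the urinalysis or dipstick limit and fall within the overlap. Albumin of at least 2.8 g/dL, the blood pressure limit and the need to swallow intact tablets narrow the group further.
- **Loss of pharmacokinetic data is a weak argument.** Section 9.6 makes evaluability depend on Cycle 1 Day 1 dosing and sampling. A later hold could affect only later samples.

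What the reply does not remove is the inconsistency: one section admits a patient at a level that another treats as grounds for interruption.

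**Conclusion.** The point holds as a narrow inconsistency between Section 3.2.7.2 and Sections 5.1.1 and 5.4. The limits agree only at 526 mg/day of creatinine. A child up to about 20 kg with 24-hour protein just under 1000 mg would be eligible with a UPC above 1.9.

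The 526 mg figure follows from the protocol alone. The weights and UPC values rest on assumed creatinine excretion, but for the smallest children the conclusion is the same over the whole range tried and under the cross-check. The protocol gives no basis for estimating how many patients this concerns; my judgment is that the number is small. No endpoint, sample size or error rate depends on it. It merits correction because the remedy is cheap and the protocol should not admit a patient at a level that it grades as Grade 3. I take no view on which limit is right.

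**What to change.** Reconcile Section 3.2.7.2 with Sections 5.1.1 and 5.4 by adding a size-independent condition to the 24-hour override. It could be a spot UPC, which Section 5.4 already uses, or 24-hour protein per m². A UPC condition matches the on-treatment unit directly; a per-m² limit would need a stated assumption about creatinine excretion. The sponsor sets the value, so that no patient is eligible at a level that the protocol grades as Grade 3.

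The condition should be added to the 1000 mg limit and not replace it. At 60 kg, UPC 1.9 corresponds to 1.9 × 60 × 15 = 1710 mg to 1.9 × 60 × 20 = 2280 mg per day (15 to 20 mg/kg/day assumed). Substituting a UPC limit near 1.9 would therefore loosen entry for larger patients.

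The sections that reuse the entry criteria should be checked at the same time: Section 4.1.1 (recovery before dose reduction), Section 4.1.3 (starting a cycle) and Section 5.3 (recovery to eligibility parameters or baseline), alongside Section 5.4's own UPC rule for resuming.

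The cost is a short text change and, if UPC is chosen, one spot urine test for patients who use the override. A few small children with heavy proteinuria would no longer qualify, and the cycle-start and recovery criteria would change with the entry rule.

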### 3.2.7.5 Central Nervous System Function Defined As:

- Patients with a known seizure disorder who are receiving non-enzyme inducing anticonvulsants and have well-controlled seizures may be enrolled. See [Appendix VII](#) for a list of recommended non-enzyme inducing anticonvulsants.
- CNS toxicity  $\leq$  Grade 2 with the exception of decreased tendon reflex (DTR). Any grade of DTR is eligible.

### 3.2.7.6 Adequate Blood Pressure Control defined as:

A blood pressure (BP)  $\leq$  the 95th percentile for age, height, and gender for pediatric patients < 18 years old ([Appendix V](#)) and  $\leq$  140/90 mmHg for patients  $\geq$  18 years old. BP should be measured as described in [Section 5.5](#), and patients should not be receiving medication for treatment of hypertension (except patients with Wilms tumor and RCC who may be eligible if on stable doses of no more than one anti-hypertensive medication with a baseline BP  $\leq$  ULN for pediatric patients and  $\leq$  140/90 for adult patients). Please note that 3 serial blood pressures should be obtained and averaged to determine baseline BP.

### 3.2.7.7 Adequate Coagulation Defined as:

- INR  $\leq$  1.5

### 3.2.7.8 Adequate Pancreatic Function Defined as:

- Serum amylase  $\leq$  1.5 x ULN
- Serum lipase  $\leq$  1.5 x ULN

## 3.3 Eligibility: Exclusion Criteria

**Important note: The exclusion criteria listed below are interpreted literally and cannot be waived. All clinical and laboratory data required for determining eligibility of a patient enrolled on this trial must be available in the patient's medical/research record. These source documents must be available for verification at the time of audit.**

### 3.3.1 Pregnancy or Breast-Feeding

Pregnant or breast-feeding women will not be entered on this study due to risks of fetal and teratogenic adverse events as seen in animal/human studies. Pregnancy tests must be obtained in girls who are post-menarchal. Males or females of reproductive potential may not participate unless they have agreed to use two methods of birth control- a medically accepted barrier method of contraceptive method (e.g., male or female condom) and a second effective method of birth control- during protocol therapy and for at least 4 months after the last dose of XL184. Abstinence is an acceptable method of birth control.

